9.5.2 Safety variables

All safety data will be summarized for the SAF.

Safety summaries will be primarily based on on-treatment data with selected tables also presented for the all data after the first intake of study drug, while all data based safety data will be listed.

Secondary safety endpoints

The secondary endpoint of the rate of patients with at least one treatment emergent AE by primary system organ class will be presented descriptively and analyzed using a Cox regression model in a similar manner as the primary endpoint. A supportive analysis on the rate of patients with at least one AE by primary system organ class will be conducted similarly including all AEs starting on or after the time of the first intake of study drug (i.e., treatment emergent AEs and AEs occurring during the post-treatment follow-up).

The secondary endpoint of the rate of treatment emergent patient deaths and patient hospitalizations (any visit to the hospital requiring an overnight stay or an emergency room visit greater than 24 hours) due to an asthma exacerbation will be analyzed using a negative binomial regression model. The model will include randomization stratum (as in the analysis on primary endpoint), treatment group, severity of asthma (GINA steps 3, 4 and 5), and region as fixed class effects, with the natural logarithm of the duration of on-treatment follow-up in years as an offset variable. The duration of on-treatment follow-up in years will be calculated

for each patient as (treatment end date - treatment start date + 2 days)/365.25 without taking into account treatment interruptions. A supportive analysis of the rate of patient deaths and patient hospitalizations due to asthma exacerbations treatment emergent and after treatment discontinuation will be conducted similarly with the natural logarithm of the duration of follow-up in years as an offset variable.

In addition to the inferential analysis, summary statistics on the secondary safety variables will be presented as described below.

Adverse events

Adverse events after informed consent including asthma exacerbations will be summarized and listed. Summaries will include the number of patients with an event, exposure-adjusted incidence rates (patients with an event per patient year of follow-up to first event or censoring) and the percentage of patients with an event.

The following treatment emergent AE summaries will be produced:

- overall by system organ class and preferred term,

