1.2.2 Secondary objective(s)

Treatment Period 1 (52-week treatment period):

[figure not shown]
In patients with moderate-to-severe asthma receiving SoC asthma therapy, to evaluate the long-term safety of QAW039 (150 mg once daily and 450 mg once daily), compared with placebo, as assessed by:

- the rate of patients with at least 1 treatment emergent AE by primary system organ class; and
- the rate of treatment emergent patient deaths and patient hospitalizations (any visit to the hospital requiring an overnight stay or an emergency room visit greater than 24 hours) due to an asthma exacerbation.

Treatment Period 1 and Treatment Period 2 combined:

In patients with moderate-to-severe-asthma receiving SoC asthma therapy, to evaluate the long-term safety of QAW039 (150 mg once daily and 450 mg once daily), compared with placebo, as assessed by:

- the rate of patients with at least 1 treatment emergent AE by primary system organ class; and
- the rate of treatment emergent patient deaths and patient hospitalizations (any visit to the hospital requiring an overnight stay or an emergency room visit greater than 24 hours) due to an asthma exacerbation.

2 Statistical methods

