2.5.2 Statistical hypothesis, model, and method of analysis

The time-to-first treatment emergent AE will be considered from the start of study treatment for Study A2315 only and the clinical study report will be based solely on the data from Study A2315.

The primary variable will be analyzed by a Cox regression model stratified by randomization stratum (but not by region):

- patients on QAW039 150 mg once daily treatment in Studies QAW039A2307, QAW039A2314,
- patients on QAW039 450 mg once daily treatment in Studies QAW039A2307 and QAW039A2314,
- patients on placebo in Studies QAW039A2307 and QAW039A2314
- patients on QAW039 150 mg once daily treatment in Studies QAW039A2316 and QAW039A2317,
- patients on placebo in Studies QAW039A2316 and QAW039A2317,
- patients who have not previously participated in a study of QAW039,

and treatment group, severity of asthma (GINA treatment steps 3, 4, and 5), and region as fixed class effects.

Hazard ratios comparing QAW039 450 mg once daily, QAW039 150 mg, once daily, and placebo treatments with regard to time to first treatment emergent AEs and their corresponding 95% profile likelihood confidence intervals (CIs) will be presented. Time to first treatment emergent SAEs and time to first treatment emergent AEs leading to study treatment discontinuation, will be analyzed in a similar fashion.

If the model does not converge, then the primary variable will be analyzed similar to the primary analysis but after removing stratification factors from the model. Hence in case of non-convergence, primary variable will be analyzed by a Cox regression model having treatment group, severity of asthma (GINA treatment steps 3, 4, and 5), and region as fixed class effects. If then also the model does not converge the variable will be analyzed after removing region as a fixed class effect in the model. If the resulting model also fails to converge then the variable will be analyzed considering only treatment group as a fixed class effect in the Cox regression model. [Efron's](#) method for handling ties will be used.

Summary statistics for the primary variable(s)

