2.8.1 Adverse events (AEs)

Adverse events after informed consent including asthma exacerbations will be recorded. Adverse events that started during the study after informed consent and before the day of the first intake of study drug will be classified as prior adverse events and not included in tabulations of treatment emergent adverse events.

The following treatment emergent AE summaries will be produced by system organ class (SOC), preferred term (PT), treatment on overall population, by source of patients for:

1. all AEs,
2. all AEs by maximum severity,
3. suspected drug-related AEs,
4. AEs by standardized MedDRA query (SMQ) level
5. SAEs, and
6. AEs leading to permanent discontinuation of study-drug.

The number of patients experiencing an event, as well as the exposure-adjusted incidence rate (patients with events per 100 patient year of follow-up) will be provided in above summaries. Patient year of follow-up will be computed as (sum of the duration of exposure over patients, in days)/365.25. This method will account for the length of follow-up time under the assumption that events would occur with the same frequency at any point in time.

Summaries described above will also be produced by source of patients.

Post-treatment discontinuation AEs (events that start more than 7 days (30 days in the case of a serious AE) after the last intake of study drug) will be summarized separately in terms of number and percentage of patients with at least one AE.

Secondary endpoint: the rate of patients with at least one treatment emergent AE by primary system organ class

The number and proportion of patients with at least one treatment emergent AE by primary system organ class will be presented descriptively and analyzed using a logistic regression model stratified by randomization stratum (but not by region) and treatment group, severity of asthma (GINA treatment step 3, 4, and 5), and region as fixed class effects. Estimates of the odds ratios between QAW039 groups and placebo will be displayed along with associated 95% confidence intervals. Firth's penalized likelihood will be utilized for logistic regression for rare events.

Secondary endpoint: the rate of treatment emergent severe asthma exacerbation episodes requiring hospitalizations

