In safety analysis, each record of asthma exacerbation episode will be considered as an adverse event regardless of the interval between two episodes, i.e., no collapsing of multiple records (this differs from how asthma exacerbations are included in efficacy analyses – see Section 2.13.1). Number of treatment emergent severe asthma exacerbation episodes requiring hospitalizations (any visit to the hospital requiring an overnight stay or an emergency room visit greater than 24 hours) will be summarized by source of patients.

Adverse events of special interest / grouping of AEs

AEs of special interest definitions are found in the compound electronic Case Retrieval Strategy (eCRS). The classification reflects the current version of the dSPP and might be updated based on review of accumulating data. To identify AEs of special interest at the time of the final analysis, the latest version of the eCRS where Core safety topic risk (SP) = 'Yes' or Other Search risk (OS) = 'Yes' will be used.

The number and percentage of patients with treatment emergent AEs of special interest will be summarized by risk category, PT, treatment on overall population and by source of patients. In addition, summaries will be provided for

- Treatment emergent AEs of special interest by maximum severity
- Treatment emergent serious AEs of special interest
- Treatment emergent AEs of special interest that are suspected to be related to study drug

AE reporting for CT.gov and EudraCT

For the legal requirements of clinicaltrials.gov and EudraCT, two required tables on treatment emergent adverse events which are not serious adverse events with an incidence greater than X% and on treatment emergent serious adverse events and SAE suspected to be related to study treatment will be provided by system organ class and preferred term on the safety set population.

If for a same patient, several consecutive AEs (irrespective of study treatment causality, seriousness and severity) occurred with the same SOC and PT:

- a single occurrence will be counted if there is ≤ 1 day gap between the end date of the preceding AE and the start date of the consecutive AE
- more than one occurrence will be counted if there is > 1 day gap between the end date of the preceding AE and the start date of the consecutive AE

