2.8.2 Deaths

The number and percentage of deaths resulting from TEAEs will be summarized by SOC and PT. All the deaths in the clinical database including those occurring during screening will be listed.

Secondary endpoint: the rate of patient deaths due to a treatment emergent asthma exacerbation

The number and percentage of deaths due to a treatment emergent asthma exacerbation will be summarized.

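### The visible SAP text on asthma hospitalizations and asthma deaths gives counts and a percentage, and does not carry forward the protocol's negative binomial rate comparison with placebo

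*SAP*

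**What the plan says.** **Protocol 9.5.2.** The rate of asthma deaths and hospitalizations "due to an asthma exacerbation will be analyzed using a negative binomial regression model". The model has randomization stratum, treatment, GINA step and region as fixed effects, and log on-treatment follow-up as offset. Description comes on top of this: "In addition to the inferential analysis, summary statistics on the secondary safety variables will be presented".

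**SAP 1.2.2.** The objective is unchanged. It is still "the rate of treatment emergent patient deaths and patient hospitalizations" due to an asthma exacerbation, compared with placebo, for both doses.

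**SAP 2.8.1.** The endpoint heading still calls it a rate. The analysis sentence gives a number of hospitalized severe episodes (any "visit to the hospital requiring an overnight stay or an emergency room visit greater than 24 hours) will be summarized by source of patients". Every episode record counts; none are collapsed.

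**SAP 2.8.2.** "The number and percentage of deaths due to a treatment emergent asthma exacerbation will be summarized".

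**SAP Section 4.** The visible bullet on this endpoint records only that deaths and hospitalizations are now presented separately. For the other secondary endpoint the same section openly records a change from Cox to logistic regression. For adverse events of special interest it records that the time-to-event analyses are dropped.

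**SAP Section 1.** Data are to be analyzed in line with section 9 of the protocol, stated in general terms.

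**The concern.** The objective is comparative and is about a rate, but the visible endpoint text yields neither a rate nor a comparison. A programmer working from 2.8.1 and 2.8.2 would produce a count table and a percentage table. The hospitalization sentence does not even name treatment group.

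No other visible model estimates this endpoint. The Cox model in SAP 2.5.2 covers "Time to first treatment emergent SAEs and time to first treatment emergent AEs leading to study treatment discontinuation", so an asthma admission enters only if it is the patient's first SAE of any kind or leads to discontinuation. The logistic model in 2.8.1 takes any adverse event within a system organ class. Repeat admissions, which 2.8.1 deliberately counts one by one, enter no visible treatment comparison.

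In a trial whose whole purpose is safety against placebo, the reader would not be shown what size of harm or benefit on asthma admissions the data can exclude.

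**Working it through.** **1. Inputs.** From the documents: N = 1,570; allocation about 3:3:1; exponential censoring 0.22 per year on placebo and 0.16 on QAW039 (Protocol 9.8, SAP 3). Arms: 1570/7 = 224 placebo, 3 × 1570/7 = 673 per dose. The documents give no event rate or power for this endpoint, so there is no planned figure to reproduce. As a check on the inputs, a Wald approximation for AEs leading to discontinuation (0.03 versus 0.045 per year) gives 6.0 and 27.4 events at 1 year and 14.2 and 67.8 at 3 years. The power is 14.4% and 28.4%, against the stated 16% and 29% for 150 mg.

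**2. Counts with no drug effect.** Mean follow-up per patient is (1 − exp(−cT))/c.

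| T (years) | Placebo | Dose arm | Null count ratio = 3 × dose/placebo |
|---|---|---|---|
| 0.5 | 0.473 | 0.481 | 3.04 |
| 1 | 0.898 | 0.924 | 3.09 |
| 3 | 2.196 | 2.383 | 3.25 |

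Even if the count table is split by arm, equal rates would show as roughly a threefold difference.

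**3. Would simple person-time rates be badly confounded by the unequal allocation across strata?** Assume 400 of the 1,000 rollovers come from A2316/A2317, prior arms are equal in size, 570 patients are new, and prior-placebo patients have R times the rate of everyone else. Applying the ratios in Protocol Table 5-1, the null rates are proportional to:
- 450 mg: (3310 + 1400R)/4710
- 150 mg: (3710 + 1000R)/4710
- placebo: (1170 + 400R)/1570

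R = 2 gives 1.034 (450 mg versus placebo) and 0.966 (150 mg versus placebo). R = 0.5 gives 0.976 and 1.024. Crude rates against placebo would therefore mislead little. The loss is the missing estimate and interval, not bias.

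**4. Precision if a rate ratio were reported.** Assumptions not in the documents: 0.02 to 0.05 events per patient-year and 0.5 to 1 year of treatment. Add 30/365.25 = 0.082 year per patient for the serious-event window. The 95% CI factor is exp(1.96 × √(1/e0 + 1/e1 + k/n0 + k/n1)), with dispersion k from 0 to 5.

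| Rate per PY | T (years) | Placebo events e0 | Per-dose events e1 | CI factor |
|---|---|---|---|---|
| 0.02 | 0.5 | 2.49 | 7.57 | 4.18–4.35 |
| 0.02 | 1 | 4.40 | 13.5 | 2.93–3.09 |
| 0.05 | 0.5 | 6.23 | 18.9 | 2.47–2.63 |
| 0.05 | 1 | 11.0 | 33.9 | 1.97–2.14 |

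Without the added 30 days, the first row becomes 4.71–4.89. With 3 years at 0.05 per patient-year (493 and 1,603 person-years, hence 24.6 and 80.2 events, k = 0), the factor is about 1.6.

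**5. Chance of no placebo events** at 0.02 per patient-year and half a year: exp(−2.49) = 0.083 with the 30 days, exp(−2.12) = 0.120 without. The exact upper 95% limit for placebo would then be 3.69/124.6 = 0.030 or 3.69/106.2 = 0.035 per patient-year.

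**The case against.** **The model may still be in force.** SAP Section 1 says analysis follows protocol section 9, and the visible Section 4 bullets name models that are dropped without naming this one. Read together, silence could mean that 9.5.2 still applies. That reading is open. But the endpoint text in 2.8.1 and 2.8.2 sets out something different, and a general pointer does not tell a programmer which to follow.

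**The relevant text may be redacted.** Some Section 4 bullets, Section 2.13 and several contents entries are blacked out. SAP 2.8.1 says of the cross-referenced 2.13.1 that "this differs from how asthma exacerbations are included in efficacy analyses", so it is unlikely to hold this safety analysis, but it cannot be checked. A reader might infer that the sponsor removed the model without disclosing it, or that no estimate exists anywhere in the SAP. The documents support neither inference.

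**Other tables partly fill the gap.** This stands in part. The SAE tables in 2.8.1 give exposure-adjusted rates by preferred term and treatment. Hospitalization makes an event serious and exacerbations are recorded as adverse events, so asthma SAE rates by arm are planned. They count patients rather than episodes and have no confidence interval or rate ratio. Exposure is tabulated by treatment, so a reader could form a crude episode rate if the counts are split by arm. The percentage for deaths already allows for unequal arm sizes.

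**A full model is fragile with few events.** Also true, and early termination could justify description only. SAP 2.5.1 invokes early termination only for combining the two periods, and the Cox and logistic models are kept.

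**Conclusion.** On the visible text, the SAP keeps a rate objective against placebo and gives it an analysis that contains neither a rate nor a comparison, in conflict with Protocol 9.5.2. What is missing is an estimate with its interval, and any comparison that uses repeat admissions. Bare counts cannot stand in, because a dose arm would show about 3.0 to 3.3 times the placebo count under no effect (half a year to 3 years, at the plan's allocation and censoring).

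A reader might also infer that the reported figures would be biased. Under the assumptions in step 3 they would not be, to any important degree, once expressed as person-time rates. The interval would be wide, roughly ×/÷2 to ×/÷5 at the assumed rates and 0.5 to 1 year of treatment, and narrower with longer exposure. Showing that width is itself useful in a safety trial.

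This should be fixed. Confidence is medium because of the redactions.

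**What to change.** **Table, in SAP 2.8.1 and 2.8.2.** By treatment group, overall and by source of patients, report hospitalized episodes, patients with at least one episode, asthma deaths, person-years, and the exposure-adjusted rate with an exact 95% CI. Count person-years over the window in which events count: (min(last dose + 30 days, final visit, death) − first dose + 1)/365.25. The patient-years now defined in 2.8.1 stop at last dose, while SAP 2.5.1 counts serious events for up to 30 days afterwards.

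**Model.** Choose one of these and write it down:
- State that the negative binomial model of Protocol 9.5.2 is fitted for the combined treatment period, with the log of follow-up over that same window as offset, and rate ratios with 95% CIs for each dose versus placebo. The protocol's own offset stops the day after last dose, so it needs this update. Deaths and hospitalizations can still be tabulated separately, as Section 4 intends.
- Or state in Section 4 that the model is withdrawn and why, and keep the rates with their CIs.

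The order in which covariates are dropped on non-convergence, and the counting of an admission that ends in death, are for the sponsor to specify.

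**Cost.** SAP wording, one table and one model; no new data. The downside is wide intervals if events are few. In the sparsest case considered there is an 8 to 12% chance of no placebo events, and only the rates with exact limits could then be reported.

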3.1 Study design

This study is a 2-treatment period, randomized, multicenter parallel-group safety study (Figure 3-1). Treatment Period 1 is a 52-week, double-blind treatment period in which QAW039 or placebo is added to GINA steps 3, 4 and 5 SoC asthma therapy. Treatment Period 2 is an optional 104-week, single-blind treatment period in which patients will receive QAW039 or placebo added to GINA steps 3, 4 and 5 SoC asthma therapy. **Note:** For the purpose of this study, single-blind will mean investigators and patients will remain blinded while all Novartis personnel will be unblinded.

Eligible patients will include patients completing a prior Phase 3 study of QAW039, as well as patients who have not previously participated in a study of QAW039.

Patients who successfully complete the treatment period of a prior Phase 3 study of QAW039 will be permitted to enter Study A2315 directly upon the completion of the treatment period of the prior study without completing an off drug follow-up period in the prior study. For these patients completing a prior Phase 3 study of QAW039, the last visit of the treatment period in the prior study and Visit 1 of Study 2315 will occur on the same day (i.e., on the last day of study drug treatment in the prior study). Additionally, for patients completing a prior Phase 3 study of QAW039, Visit 201 of Study 2315 will occur the following day (1 day after completion of the last visit of the treatment period of the prior study and Visit 1 of this study [Study A2315]) so there is not any interruption in study drug treatment.

For patients who have not previously participated in a study of QAW039, Visit 1 and Visit 201 of Study 2315 will occur approximately two weeks apart (i.e., Visit 201 should occur approximately two weeks after Visit 1 in Study 2315). This will allow for review of inclusion/exclusion criteria and laboratory values.

For Treatment Period 1 in Study A2315, an informed consent (and assent, if applicable) may be obtained within 14 days prior to or at Visit 1 and before any study-related assessments or procedures are performed. For patients who participated in a prior Phase 3 study, the consent (and assent, if appropriate) for Treatment Period 1 of Study A2315 may be obtained on the last day of the treatment period of the prior Phase 3 study.

For Treatment Period 2, an informed consent (and assent if applicable) will be obtained at Visit 301 for those patients agreeing to participate in this treatment period.

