5.4 Treatment blinding

Patients, investigator staff, persons performing the assessments, and data analysts will remain blinded to the identity of the treatment from the time of randomization until interim analyses are conducted to support regulatory submissions, using the following methods: (1) Randomization data are kept strictly confidential until the time of unblinding, and will not be accessible by anyone involved in the study with the following exceptions: the external DMC, independent of the QAW039 study team, will have access to unblinded data for the purpose of safety reviews and at the time of the interim analyses. (2) For each dose level, the identity of the treatments will be concealed by the use of placebos identical in packaging, labeling, schedule of administration, appearance, taste, and odor to QAW039. Across dose levels, a double-dummy design is used because the identity of the study drug cannot be disguised, as the drug products are visibly different.

All data up to the first interim analysis of Study A2315 will be collected with the Novartis study team being blinded to study treatment. At the time of the first interim analysis, Novartis personnel will be unblinded to treatment in order to facilitate worldwide Marketing Authorization Application/New Drug Application (MAA/NDA) filings while investigators and patients will remain blinded to treatment through the remainder of the study. Additional, interim analyses, as regarded appropriate, may be conducted (e.g., to provide additional data for regulatory submissions). Study modifications are not planned based on any interim analysis.

Unblinding will only occur in the case of patient emergencies (see [Section 5.5.10](#)), at the time of interim analyses (see [Section 9.7](#)), and at the conclusion of the study. In addition, the independent DMC will be unblinded for the purpose of safety reviews.

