- investigational treatment interrupted/withdrawn
- concomitant medication or non-drug therapy given
- patient hospitalized/patient's hospitalization prolonged
- its outcome (not recovered/not resolved; recovered/resolved; recovering/resolving, recovered/resolved with sequelae; fatal; or unknown)

Once an adverse event is detected, it should be followed until its resolution or until it is judged to be permanent, and assessment should be made at each visit (or more frequently, if necessary) of any changes in severity, the suspected relationship to the study drug, the interventions required to treat it, and the outcome.

Information about common side effects already known about the investigational drug can be found in the Investigator Brochure (IB). This information will be included in the patient informed consent and should be discussed with the patient during the study as needed. Any new information regarding the safety profile of the medicinal product that is identified between IB updates will be communicated as appropriate, for example, via an Investigator Notification or an Aggregate Safety Finding. New information might require an update to the informed consent and has then to be discussed with the patient.

The investigator should also instruct each patient to report any new adverse event (beyond the protocol observation period) that the patient, or the patient's personal physician, believes might reasonably be related to study treatment. This information should be recorded in the investigator's source documents; however, if the AE meets the criteria of an SAE, it must be reported to Novartis.

Adverse events of special interest are being evaluated in this study population. Definitions are provided in [Appendix 3](#).

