7.5 Idiosyncratic drug reactions monitoring

IDRs are adverse drug reactions that do not occur in most patients (i.e., they are rare, occurring 1 in 10,000 to 1 in 100,000 patients) and do not result from known pharmacological effects of a drug. Their onset is unpredictable and they may involve one or more organ systems, most notably the immune system, liver and blood cells.

The investigator should pay special attention to any adverse events which may be a potential IDR reported by a patient. If such an event occurs, the investigator should report the event as per standard adverse event reporting procedures (i.e., serious adverse events for those meeting serious criteria and non-serious adverse events for those meeting non-serious adverse event criteria as defined in the protocol).

The investigator may also be contacted by Novartis regarding AEs that may resemble an IDR. A list of terms considered IDRs is provided in [Appendix 3](#).

Events with potential to be IDRs will be identified through a pre-specified search algorithm based on the Standardized MedDRA Queries as described in the study analysis plan. These events will be reviewed by the DMC on a regular basis.

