- overall by system organ class, preferred term and maximum severity,
- suspected drug-related AEs by system organ class and preferred term,
- SAEs by system organ class and preferred term, and
- AEs leading to permanent discontinuation of study-drug by system organ class and preferred term.

Additionally, summaries including both treatment emergent and post-treatment discontinuation events will be produced for AEs and SAEs by system organ class and preferred term. Similarly, summaries will also be presented on patient deaths and patient hospitalizations (any visit to the hospital requiring an overnight stay or an emergency room visit greater than 24 hours) due to an asthma exacerbation.

The number and percentage of patients with treatment emergent AEs of special interest (e.g., IDRs), will be summarized for each type of event with a break-down for each type of event by SMQ (when applicable) and preferred term. Time-to-first-event analyses using Kaplan-Meier plots and Cox regressions with the same model terms as the primary efficacy analysis model will be reported for each type of event, as well as incidence for recurrent events per patient-year of follow-up. The strategy for identifying these events will be defined in the detailed statistical analysis plan for this study.

Vital signs

On-treatment data from the vital signs (body temperature, systolic blood pressure, diastolic blood pressure, and pulse rate) will be summarized by treatment and scheduled visit. The maximum and minimum on-treatment systolic blood pressure, diastolic blood pressure, and pulse rate post-baseline (including values from post-baseline unscheduled and premature discontinuation visits) will also be summarized by treatment. Absolute on-treatment body weight will be summarized by scheduled visit. The on-treatment change from baseline to each scheduled post-baseline visit will be summarized by vital sign parameter, scheduled visit and treatment with standard descriptive statistics.

Notable on-treatment values and notable on-treatment changes from baseline in vital signs will be summarized.

Electrocardiogram (ECG)

The on-treatment changes from baseline will be summarized by ECG parameter, scheduled visit where baseline and post baseline values are both available.

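### SAP 2.8.1 leaves the search for adverse events of special interest open to updates until the final analysis, with no dated reference version and no blinding condition

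*SAP*

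**What the plan says.** **What the protocol commits to.** Section 7.1 states: "Adverse events of special interest are being evaluated in this study population. Definitions are provided in" Appendix 3, which lists groups of potential IDRs. For possible IDRs, section 7.5 requires that they are to be found by a set search; in its words, "identified through a pre-specified search algorithm based on the Standardized MedDRA Queries as described in the study analysis plan". Section 9.5.2 covers AESIs more widely, with IDRs as the example: "The strategy for identifying these events will be defined in the detailed statistical analysis plan for this study".

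**What the SAP does.** The AESI paragraph of SAP 2.8.1 contains no algorithm, query list or term list. It refers to the compound eCRS and adds: "The classification reflects the current version of the dSPP and might be updated based on review of accumulating data". The operative rule begins "To identify AEs of special interest at the time of the final analysis, the latest version of the eCRS" and restricts that version to entries flagged as a core safety topic or as another search risk.

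**Who is blinded.** For Treatment Period 2, protocol 3.1 defines the term used there: "single-blind will mean investigators and patients will remain blinded while all Novartis personnel will be unblinded". SAP 1.1.1 repeats this. Protocol 5.4 adds: "At the time of the first interim analysis, Novartis personnel will be unblinded to treatment". During Treatment Period 1, sponsor personnel monitoring the study are blinded unless an interim analysis takes place (protocol 3.1).

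**What is declared as changed.** The visible part of SAP section 4 says AESIs will be presented descriptively only, without the Kaplan-Meier and Cox analyses of protocol 9.5.2. It does not mention a change in how AESIs are identified.

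**The concern.** A special-interest category is a grouping of preferred terms, and its count depends on which terms are in the group. If the grouping can be revised after those revising it may know which arm each event fell in, then a difference between arms in that category no longer has the standing of a comparison set in advance. This holds even if every revision is made in good faith.

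It matters more here because SAP section 4 removes the modelled AESI analyses, so the category counts are all that remains of the AESI evaluation. IDRs are also a named question for this compound: protocol 3.6 raises them because of the acyl glucuronide metabolite. Without a dated reference version, a reader of the study report cannot separate the categories as they stood before unblinding from those shaped afterwards.

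**Working it through.** No arithmetic applies. The plan gives no expected count, interval, test or power for AESIs, so there is no figure to reproduce. The check is a comparison of texts.

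| Question | Protocol | SAP (visible text) |
|---|---|---|
| Where is the search defined? | In the analysis plan (7.5 for IDRs; 9.5.2 for the AESI strategy) | In the eCRS, outside the SAP (2.8.1) |
| Is it set in advance? | Yes, explicitly for IDRs (7.5); for AESIs generally only a strategy is promised (9.5.2) | A selection rule is stated, but the content it selects is the latest version and may change with accumulating data (2.8.1) |
| Is there a version, date or freeze point? | Left to the SAP | None |
| Must updates be blind to treatment? | Not addressed | Not addressed |
| Is the departure declared? | – | Not in the visible part of section 4 |

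1. *Commitment.* For IDRs the protocol promises a pre-specified algorithm described in the SAP. For AESIs as a class it promises that the SAP will define the strategy, which is weaker.
2. *Delivery.* The flag rule in SAP 2.8.1 is a strategy of a kind, so 9.5.2 is met in form. The content is neither in the SAP nor tied to a date, so 7.5 is not met in the visible text.
3. *Timing against unblinding.* Updates are allowed up to the final analysis. SAP 2.5.1 states that the study was terminated early and analyses both treatment periods combined. The window for updates can therefore include Treatment Period 2, when all sponsor personnel are unblinded, and any time after a first interim analysis.
4. *Comparison within the documents.* SAP 6.2 ties the MedDRA version to database lock. Protocol 9.1 has major protocol deviations defined before database lock and unblinding. The eCRS has neither anchor.
5. *Reach.* The primary endpoints are times to first treatment-emergent AE, SAE and AE leading to treatment discontinuation. The secondary endpoints are AEs by system organ class, and deaths and hospitalizations due to asthma exacerbation. None uses the AESI definition, so only the descriptive AESI tables are exposed.

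**The case against.** The strongest reply is that a safety search should follow what is learned about the compound, and that nothing can be hidden by it. Appendix 3 itself allows that other potential IDRs may arise. SAP 2.8.1 tabulates all treatment-emergent AEs by system organ class, preferred term and treatment, and also by standardized MedDRA query. The AESI tables are themselves broken down by preferred term. Liver criteria are set numerically in SAP Table 2-4, and QTcF criteria in Table 2-5, outside the eCRS.

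Most of this stands. An event dropped from a category remains visible elsewhere, and updating the search is legitimate. Two gaps remain. The tables do not show which terms were added or removed, or when. And the number of patients in a category cannot be rebuilt by adding preferred-term rows, because one patient may contribute to several.

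A reader might infer four stronger things that the documents do not support:

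- *That unblinded staff did reshape the categories.* The documents do not say who edits the eCRS, whether accumulating data are reviewed by arm, whether an interim analysis took place, or whether any update was made. They show that the rule permits it.
- *That both protocol sections promised a fixed algorithm.* Only 7.5 uses pre-specification, and only for IDRs.
- *That no frozen list exists.* Parts of SAP section 4 are blacked out, and section 6.3 is absent from the visible appendix, so this can be said only of the visible text.
- *That one or two terms would decide the safety conclusion.* No AESI counts are given, so any illustration would rest on invented numbers. The IDR frequency in protocol 7.5 describes true reactions, not the events a search would retrieve.

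**Conclusion.** The point holds as a limited defect of pre-specification. As visible, the SAP lets AESI categories be revised from accumulating data up to the final analysis, with no dated reference and no blinding condition, while sponsor personnel are unblinded for part of that time. This departs from protocol 7.5, sits poorly with 9.5.2, and is not declared in the visible part of SAP section 4.

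Its size is small in scope and cannot be quantified. It affects descriptive category counts only; the primary and secondary results are untouched and no event is lost from reporting. It is still worth correcting, because those counts are what is left of the AESI evaluation and the remedy costs little.

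The conclusion assumes that the redacted text neither sets a reference version nor discloses the change. If it does, the remaining task is to reconcile it with the latest-version rule in 2.8.1.

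**What to change.** In SAP 2.8.1, cite the version and date of the last eCRS in force before the first sponsor unblinding and append its search terms. The documents do not give that date, so it must come from the sponsor's records. Report the AESI category table, including the Appendix 3 IDR groups, with that version, allowing only MedDRA up-versioning. Show the latest-version table beside it, with terms added or removed since then labelled as post-unblinding changes. List the departure from protocol 7.5 and 9.5.2 in SAP section 4.

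The cost is SAP wording and one additional set of descriptive AESI tables. New safety terms are still reported through the latest-version table, so signal detection is not reduced.
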